8.2.1. Belantamab Mafodotin

8.2.1.1. Eye Disorders, Thrombocytopenia, and Infusion Related Reactions

The severity of all AESI will be graded utilizing the National Cancer Institute Common Toxicity Criteria for Adverse Events (NCI-CTCAE) v.4.03 [NCI, 2010]. For thrombocytopenia, in addition to events identified and collected in eCRF, a comprehensive list of MedDRA terms based on clinical review will be used to identify each type of event. Changes to the MedDRA dictionary may occur between the start of the study and the time of reporting and/or emerging data from on-going studies may highlight additional adverse events of special interest, therefore the list of terms to be used for each event of interest and the specific events of interest will be based on the safety review team (SRT) agreements in place at the time of reporting. For infusion related reactions (IRR), events are only considered IRR if the preferred term = “Infusion related reaction” or event was reported on an infusion day after the start of infusion or within 24 hours following end of infusion and led to a temporary interruption or prolongation of infusion time or treatment withdrawal. For keratopathy events (CTCAE) under eye disorders, events are considered keratopathy events if the synonym =

“keratopathy/keratitis”. The details of the planned displays are provided in [Appendix 11: List of Data Displays](#).

Summaries of the number and percentage of subjects with these events will be provided for each type of events separately by preferred term and maximum grade. The time of onset and duration of first occurrence of each type of events will be summarized using summary statistics mean, standard deviation, median, minimum value, and maximum. The number and percentage of subjects who have time of onset of first occurrence and the number and percentage of subjects who have duration of first occurrence will be reported in the following:

Thrombocytopenia and Eye Disorders:

- Time of first occurrence: 1-21, 22-42, 43-63, >63 days
- Duration of first occurrence: 1-21, 22-42, >42 days

Infusion Related Reactions:

- Time of first occurrence: 0-6, >6-12, >12-18, >18-24 hours
- Duration of first occurrence: 0-12, >12-24, >24 hours

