8.2.1.2. Corneal Events (GSK Scale)

After discussions with regulatory agencies, GSK developed a grading scale to capture both corneal examination findings and visual acuity changes in participants treated with belantamab mafodotin. This GSK scale differs from the CTCAE criteria for eye disorders which relies mainly on patient’s symptoms and patient’s ability to attend to ‘activities of daily living’ for grading of events.

Severity of belantamab mafodotin treatment related corneal events will also be graded using the GSK scale for corneal events and should be used for evaluation of DLT.

Summaries of the number and percentage of subjects with these events will be provided for each type of grade separately by visit. The time of onset and duration of first

occurrence of grade 2 or above events, and the event characteristics will be summarized similarly as the AESIs for belantamab mafodotin provided in Section 8.2.1.1.

In addition to the listing, the following outputs will be provided for corneal events graded using the GSK scale:

1. Overview for corneal event (GSK scale)
2. Summary of actions taken with study treatment (e.g. dose reduction/delay/study treatment withdrawn)

The details of the planned displays are provided in [Appendix 11: List of Data Displays](#).

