16.6.4. Safety

Adverse Events
AE'S of Special Interest (belantamab mafodotin)

 Corneal events (GSK Scale): collected in eCRF Eye Disorders (CTCAE) Thrombocytopenia Infusion related reactions
AE'S of Special Interest (pembrolizumab)

 Overdose

Duration of AE

 Calculated as the number of days from AE Start Date to AE Stop Date: 
 AE Start Date = Missing → Elapse Time = Missing AE Stop Date = Missing → Elapse Time = Missing Otherwise → Elapsed Time = AE Stop Date – AE Start Date + 1
ECHO/MUGA

 Change from Baseline for cardiac data, e.g., Left Ventricular Ejection Fraction (LVEF), will be calculated based on the same modality (ECHO or MUGA) throughout the study for each subject. Post-baseline assessments with a different cardiac scan modality will not be used to calculate change from Baseline.

DLT
DLT Evaluable

 Participant is considered DLT evaluable if they fulfilled the 'All Treated' population criteria during part 1 (Dose Escalation) and are followed up for a 21-day period or withdrawn within 21 days due to an AE meeting the definition of a DLT as defined in Section 4.2.3.1 of protocol.

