3.0029	All Treated	See programming notes	Summary of Keratopathy Events (CTCAE) Characteristics II	Report for: Part 1, Part 2, and combined Part 1 and Part 2; Summarize by: dose level (Refer to Section 5.1 for ordering of dose level and omit 1.92 mg/kg if data is not available), Total; Refer to mid205678 (primary_01) Table 3.0200 for guidance.	P-SAC [3], F-SAC [4]
3.0030	All Treated	ESI2a	Summary of Onset and Duration of the First Occurrence of Grade 2 or Above Corneal Events (GSK scale)	Report for: Part 1, Part 2, and combined Part 1 and Part 2; Summarize by: dose level (Refer to Section 5.1 for ordering of dose level and omit 1.92 mg/kg if data is not available), Total; Time of onset: 1-21, 22-42, 43-63, >63. Duration till resolution: 1-21, 22-42, >42.	P-SAC [3], F-SAC [4]
3.0031	All Treated	ESI2a	Summary of Onset and Duration of the First Occurrence of Eye Disorders (CTCAE)	Report for: Part 1, Part 2, and combined Part 1 and Part 2; Summarize by: dose level (Refer to Section 5.1 for ordering of dose level and omit 1.92 mg/kg if data is not available), Total; Time of onset: 1-21, 22-42, 43-63, >63. Duration till resolution: 1-21, 22-42, >42.	P-SAC [3], F-SAC [4]
3.0032	All Treated	ESI2a	Summary of Onset and Duration of the First Occurrence of Thrombocytopenia	Report for: Part 1, Part 2, and combined Part 1 and Part 2; Summarize by: dose level (Refer to Section 5.1 for ordering of dose level and omit 1.92 mg/kg if data is not available), Total; Time of onset: 1-21, 22-42, 43-63, >63. Duration till resolution: 1-21, 22-42, >42.	P-SAC [3], F-SAC [4]

Safety: Tables					
No.	Population	IDSL / Example Shell	Title	Programming Notes	Deliverable [Priority]
3.0033	All Treated	ESI2a	Summary of Onset and Duration of the First Occurrence of Infusion Related Reactions	Report for: Part 1, Part 2, and combined Part 1 and Part 2; Summarize by: dose level (Refer to Section 5.1 for ordering of dose level and omit 1.92 mg/kg if data is not available), Total; Time of onset: 1-21, 22-42, 43-63, >63. Duration till resolution: 1-21, 22-42, >42.	P-SAC [3], F-SAC [4]
3.0034	All Treated	See programming notes	Summary of Corneal Events (GSK scale) by Grade and Visit	Report for: Part 1, Part 2, and combined Part 1 and Part 2; Summarize by: dose level (Refer to Section 5.1 for ordering of dose level and omit 1.92 mg/kg if data is not available) Total. Include Worst-case baseline visit.; Refer to mid205678 (primary_01) Table 3.0340 for guidance.	P-SAC [3], F-SAC [4]

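### First-occurrence AESI and neutropenia durations are summarised among resolved events only, with no censoring and no stated count of unresolved events, which biases them downward

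*SAP*

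**What the plan says.** The derivation rule is in SAP Section 16.6.4 (Duration of AE). With both dates present, "Otherwise → Elapsed Time = AE Stop Date – AE Start Date + 1". Without a stop date, "AE Stop Date = Missing → Elapse Time = Missing". Section 16.7.2.1 adds that imputed partial dates are not used for durations, so a partial stop date does not supply one either.

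Section 8.2.1.1 (eye disorders, thrombocytopenia, infusion related reactions) states the summary: "duration of first occurrence of each type of events will be summarized using summary statistics mean, standard deviation, median, minimum value, and maximum". It adds a banded count in which "the number and percentage of subjects who have duration of first occurrence will be reported in the following". For thrombocytopenia and eye disorders the bands are "Duration of first occurrence: 1-21, 22-42, >42 days". Section 8.2.1.2 carries this over to corneal events on the GSK scale: "occurrence of grade 2 or above events, and the event characteristics will be summarized similarly as the AESIs for belantamab mafodotin provided in Section 8.2.1.1". Section 8.2.1.3 does the same for neutropenia.

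The displays are Tables 3.0030 ("Summary of Onset and Duration of the First Occurrence of Grade 2 or Above Corneal Events (GSK scale)"), 3.0031 (eye disorders), 3.0032 (thrombocytopenia) and 3.0041 (neutropenia). All four are due at the primary and the final analysis, with the programming note "Duration till resolution: 1-21, 22-42, >42".

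The text gives no censoring rule for events still open and no unresolved band. The event characteristics listed in Section 8.2.1.1 cover seriousness, relatedness, number of occurrences, maximum grade and action taken. They do not name outcome.

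**The concern.** An event that is open when observation ends has a right-censored duration: it has already lasted some time and will last longer. Setting it to missing removes it from the mean, the median and the bands. The removal is informative, because for a given length of observation a long event is more likely to be open than a short one. The remaining durations therefore lean short.

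Two other provisions add to this. Section 8.2.1.1 treats overlapping events as one occurrence, so one open component can keep the whole occurrence open. Under Section 16.7.1, data collection stops at the post-analysis continued treatment stage for participants no longer on study treatment. Events still open in those participants then never acquire a duration, and the final analysis does not necessarily repair what the primary analysis omits.

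At stake is the description of how long corneal, eye and haematological toxicity lasts. No hypothesis test or stopping rule uses it.

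**Working it through.** **Figure to reproduce.** The SAP states no duration, unresolved share or event count on this point. The check traces the rule to the tables and then illustrates the bias under stated assumptions.

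**Tracing the rule.** No stop date gives no duration (Section 16.6.4). The mean, median and bands use durations (Section 8.2.1.1, extended by 8.2.1.2 and 8.2.1.3). Tables 3.0030-3.0032 and 3.0041 therefore describe resolved first occurrences. By contrast, the SAP's own duration of response (Section 7.2.2.2) is estimated by Kaplan-Meier, with responders who have not progressed censored.

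**Inputs from the SAP.** The bands, with 42 days as the upper cut. The primary analysis at about 15 months from last subject first visit (Section 2.3). At least 24 months from last subject first dose by end of study (Section 16.7.1).

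**Inputs assumed, because the SAP gives none.** True durations T are exponential with median m. Observation time after onset, C, is uniform from a to b days and independent of T. An event is resolved if T ≤ C.

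**Formulas.** With λ = ln 2 / m:
- Unresolved share: U = [2^(−a/m) − 2^(−b/m)] / [λ(b − a)].
- Resolved-only median: the t at which ∫₀ᵗ λe^(−λu) P(C ≥ u) du = (1 − U)/2.
- True share over 42 days: 2^(−42/m).

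**One case in full.** Take m = 90, a = 30, b = 450. Then λ = 0.6931/90 = 0.007702 and U = (0.7937 − 0.0313)/(0.007702 × 420) = 0.7624/3.2347 = 0.236. The median equation solves at t ≈ 64 days, against a true 90. The share over 42 days is 64%, against a true 2^(−42/90) = 72%.

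**Range.**

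| True median | Observation after onset (days) | Unresolved | Resolved-only median | Share >42 days, resolved-only (true) |
|---|---|---|---|---|
| 21 | 30-120 | 12% | 18 | 16% (25%) |
| 21 | 30-450 | 3% | 20 | 23% (25%) |
| 21 | 30-730 | 2% | 21 | 24% (25%) |
| 90 | 30-120 | 57% | 31 | 36% (72%) |
| 90 | 30-450 | 24% | 64 | 64% (72%) |
| 90 | 30-730 | 15% | 74 | 68% (72%) |
| 180 | 30-120 | 75% | 34 | 41% (85%) |
| 180 | 30-450 | 44% | 90 | 73% (85%) |
| 180 | 30-730 | 31% | 116 | 79% (85%) |

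**A favourable case.** Suppose every event starts on day 42 and is followed to 15 months, about 414 days. With m = 90 the unresolved share is 2^(−414/90) = 4%. The resolved-only median solves 1 − 2^(−t/90) = 0.959/2, which gives t ≈ 85 days. The bias is then small.

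**After the fix.** In simulations of 200,000 events per scenario (medians 21, 42, 90 and 180 days; observation 30-120, 30-365 and 30-730 days), Kaplan-Meier with unresolved events censored recovered the assumed median in every scenario but one. In that one (median 180, observation 30-120) the median was not reached.

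**The case against.** The strongest reply is that the plan names its statistic and makes the omission partly visible. The programming notes speak of duration until resolution, a quantity defined only for events that resolved. Section 8.2.1.1 reports how many subjects have a duration, and the characteristics tables (3.0023, 3.0024, 3.0026, 3.0040) report how many had the event, so a reader can subtract. Ocular persistence also appears elsewhere: corneal events by grade and visit (Table 3.0034), time to re-initiation after a hold (Table 3.0038), outcome and time to resolution for definite visual acuity worsening (Section 8.5), and individual listings. The mock shells are not in the document, so an outcome row in the standard displays cannot be ruled out. All of this is descriptive safety reporting in about 12 + 28 subjects.

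These points stand, and they limit the consequence. They do not correct the mean, the median or the band percentages. Subtraction gives the number without a duration, but does not separate open events from events with an incomplete date.

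Two stronger readings are tempting, and the documents support neither. A reader might infer that duration is estimated from short events alone. It is not: any event with full dates counts however long it lasted, and the >42-day band holds long events that resolved. A reader might also infer that most events will be open at the primary cut. The SAP gives no such figure, and follow-up of about 15 months from last subject first visit argues against assuming it.

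**Conclusion.** The point holds as a bias of known direction and unknown size. Followed as written, Section 16.6.4 restricts the first-occurrence duration summaries for corneal events, eye disorders, thrombocytopenia and neutropenia to resolved events, and this pulls the mean, the median and the >42-day share downward.

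The size depends on how fast events resolve and how long they are observed after onset, and the SAP gives neither. Under exponential durations with independent observation time, events with a true median of 21 days show a resolved-only median of 18 to 21 days, which is negligible except with short observation. With a true median of 90 days the resolved-only median runs from 31 days (observation 30-120) to about 85 days (fixed 414 days). Slow-resolving toxicity and early death or withdrawal are therefore the cases to worry about. Haematological events that clear quickly are not.

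The primary endpoint is untouched. This is a worthwhile, inexpensive improvement to a safety summary.

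**What to change.** In Tables 3.0030-3.0032 and 3.0041:

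1. Report the number and percentage of first occurrences unresolved at last assessment, separately from those lacking a duration because of an incomplete date.
2. Estimate time from onset to resolution of the first occurrence by Kaplan-Meier, censoring unresolved events at last assessment, data cut-off or death. Give the median with its confidence interval and the proportion unresolved at days 21 and 42, which match the existing bands.
3. Keep the existing mean, median and bands, labelled as among resolved events.

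State the censoring rule beside the duration derivation in Section 16.6.4 and refer to it from Sections 8.2.1.1 to 8.2.1.3.

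The cost is a few lines of SAP text and a little extra programming, with a method the SAP already uses and no new data collection. The downside is that estimates in small dose groups will be wide or not reached. In those groups the count of unresolved events carries most of the information.

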16.6.5. Patient Reported Outcomes

[figure not shown]
16.6.5.1. EORTC QLQ-C30

The EORTC QLQ-C30 is a 30-item questionnaire containing both single- and multi-item measures [Aaronson, 1993]. These include five functional scales (Physical, Role, Cognitive, Emotional, and Social Functioning), three symptom scales (Fatigue, Pain, and Nausea/Vomiting), a Global Health Status/QoL scale, and six single items (Constipation, Diarrhea, Insomnia, Dyspnea, Appetite Loss, and Financial Difficulties). The below image shows the details.

CONFIDENTIAL

205207

CCI - This section contained Clinical Outcome Assessment data collection questionnaires or indices, which are protected by third party copyright laws and therefore have been excluded.

Technical Summary

In practical terms, if items I_1, I_2, \dots, I_n are included in a scale, the procedure is as follows:

Raw score

Calculate the raw score

$$RawScore = RS = (I_1 + I_2 + \dots + I_n)/n$$

Linear transformation

Apply the linear transformation to 0-100 to obtain the score S ,

$$\text{Functional scales: } S = \left\{ 1 - \frac{(RS - 1)}{\text{range}} \right\} \times 100$$

$$\text{Symptom scales / items: } S = \{ (RS - 1)/\text{range} \} \times 100$$

$$\text{Global health status / QoL: } S = \{ (RS - 1)/\text{range} \} \times 100$$

Range is the difference between the maximum possible value of RS and the minimum possible value. The QLQ-C30 has been designed so that all items in any scale take the same range of values. Therefore, the range of RS equals the range of the item values. Most items are scored 1 to 4, giving *range* = 3. The exceptions are the items contributing to the global health status / QoL, which are 7-point questions with *range* = 6, and the initial yes/no items on the earlier versions of the QLQ-C30 which have *range* = 1.

Scoring of the QLQ-C30 Summary Score

The EORTC QLQ-C30 Summary Score is calculated from the mean of 13 of the 15 QLQ-C30 scales (the Global Quality of Life scale and the Financial Impact scale are not included). Prior to calculating the mean, the symptom scales need to be reversed to obtain a uniform direction of all scales. The summary score should only be calculated if all of the required 13 scale scores are available.

$$\text{QLQ-C30 Summary Score} = [\text{Physical Functioning} + \text{Role Functioning} + \text{Social Functioning} + \text{Emotional Functioning} + \text{Cognitive Functioning} + (100 - \text{Fatigue}) + (100 - \text{Pain}) + (100 - \text{Nausea_Vomiting}) + (100 - \text{Dyspnoea}) + (100 - \text{Sleeping Disturbances}) + (100 - \text{Appetite Loss}) + (100 - \text{Constipation}) + (100 - \text{Diarrhoea})]/13.$$

Handling of missing items

Single-item measures: if the item is missing, the score S will be set to missing.

Scales requiring multiple items: if at least half of the items from the scale are available, the score S will be calculated based on available items. If more than half of the items from the scale are missing, the score S will be set to missing (Fayers et. al., The EORTC QLQ-C30 Scoring Manual (3rd Edition) 2001).

Minimal Important Difference (MID)

[figure not shown]
In a sample of patients who received chemotherapy for either breast cancer or small-cell lung cancer (n=246, n=80 respectively), the mean change in EORTC QLQ-C30 score

between baseline and follow-up was about 5 to 10 points on a 0-100 scale for patients who indicated “a little” change on the Subjective Significance Questionnaire (SSQ), either for better or for worse (Osoba, 1998).

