13.2.2. Ocular Surface Disease Index

The Ocular Surface Disease Index (OSDI) is a 12-item questionnaire designed to assess both the frequency of dry eye symptoms and their impact on vision-related functioning [Schiffman, 2000]. The OSDI has demonstrated good reliability, validity, sensitivity, and specificity, and can be used as a complement to other clinical and subjective measures of dry eye disease by providing a quantifiable assessment of dry eye symptom frequency and the impact of these symptoms on vision-related functioning.

For the OSDI, the total score will be calculated as well as scores for the three subscales (ocular symptom: item 1-3; vision-related function: item 4-9; and environmental triggers: item 10-12).

The total OSDI score = ([sum of scores for all questions answered \times 100]/[total number of questions answered \times 4]). Subscale scores are computed similarly with only the questions from each subscale used to generate its own score. Subscale scores are computed similarly with only the questions from each subscale used to generate its own score. A score of 100 corresponds to complete disability (a response of “all of the time” to all questions answered), while a score of 0 corresponds to no disability (a response of “none of the time” to all questions answered). Therefore, decrease in score from baseline means improvement.

For each of the three sub-scales, the descriptive summary of the actual value and change from baseline at selected time points will be provided. For the Vision-Related Functioning domain, the number and percentage of participants with post-baseline score worsening of ≥ 12.5 from baseline score will be summarized at selected time points. Additionally, a time to event analysis of time to meaningful worsening based on the ≥ 12.5 threshold will be summarized with frequency of number of patients with event (N, %). Time to first event and duration of event will also be calculated (median days, range). Additionally, recovery from first event defined as ≥ 12.5 decrease from the first worst score will be summarized.

Plots of mean change from baseline (including baseline) and 95% confidence interval over time by visit, and at end of study treatment, last follow-up, and worst case post-baseline for individual domains will also be provided. The overall total score and sub-scale scores will be listed.

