13.3. Value Evidence and Outcome (Part 2 only)

13.3.1. European Organization for Research and Treatment of Cancer Quality of Life Questionnaire 30-item Core module (EORTC QLQ-C30)

The EORTC QLQ-C30 is a 30-item questionnaire containing both single- and multi-item measures [Aaronson, 1993]. These include five functional scales (Physical, Role, Cognitive, Emotional, and Social Functioning), three symptom scales (Fatigue, Pain, and Nausea/Vomiting), a Global Health Status/QoL scale, and six single items (Constipation, Diarrhea, Insomnia, Dyspnea, Appetite Loss, and Financial Difficulties). Scores for each scale and single-item measure are averaged and transformed linearly to a score ranging from 0–100. Details of deriving domain scores (9 scales and 6 single items) and summary score can be found in Section [16.6.5.1](#).

A high score for functional scales and for Global Health Status/QoL represent better functioning ability or Health-Related Quality of Life (HRQoL), (higher score indicates improvement) whereas a high score for symptom scales and single items represents significant symptomatology [Proskorovsky 2014]. (lower score indicates improvement)

Descriptive summaries (mean, SD, median, min and max) of the actual value and change from baseline at selected time points will be provided for EORTC QLQ-C30 summary score and each domain score.

Plots of mean change from baseline (including baseline) and 95% confidence interval over time by visit, and at end of study treatment, last follow-up, and worst case post-baseline for individual domains will also be provided. The overall summary score and 11-sub-scale scores will be listed.

13.3.2. European Organization for Research and Treatment of Cancer Quality of Life Questionnaire 20-item Multiple Myeloma module (EORTC QLQ-MY20)

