				It requires at least one day gap between the resolution of worsening from first course to the onset of second course.	
NEI-VFQ-25					
6.004	All Treated	See programming notes	Summary of Change in NEI-VFQ-25 Subscale Scores from Baseline	Report for: Part 1, Part 2, and combined Part 1 and Part 2; Summarize by: dose level (Refer to Section 5.1 for ordering of dose level and omit 1.92 mg/kg if data is not available). Refer to mid205678 (primary_01) Table 8.0110 for guidance. Including 11 subscale score. Additional timepoints includes EOT visit, last follow-up visit, and worst change from baseline; include both investigator and subject assessed data	P-SAC [3], F-SAC [4]
EORTC QLQ-C30					
6.005	All Treated	See programming notes	Summary of Change in EORTC QLQ-C30 Domain Scores from Baseline (Part 2)	Report for: Part 2; Refer to mid205678 (primary_01) Table 8.0020 for guidance. Including score for 15 domains and Improvement in EORTC QLQ-C30 domain score >=10	P-SAC [3], F-SAC [4]

Health Outcomes: Tables					
No.	Population	IDSL / Example Shell	Title	Programming Notes	Deliverable [Priority]
EORTC QLQ-MY20					
6.006	All Treated	See programming notes	Summary of Change in EORTC QLQ-MY20 Domain Scores from Baseline (Part 2)	Report for: Part 2; Refer to mid205678 (primary_01) Table 8.0070 for guidance. Including score for 4 domains and Improvement in EORTC QLQ-MY20 domain score >=10	P-SAC [3], F-SAC [4]
Compliance of PRO-CTCAE, OSDI, and EORTC QLQ-C30					
6.007	All Treated	See programming notes	Summary of Compliance of OSDI by Visit	Report for: Part 1, Part 2, and combined Part 1 and Part 2; Summarize by: dose level (Refer to Section 5.1 for ordering of dose level and omit 1.92 mg/kg if data is not available). Refer to mid205678 (primary_08) Table 8.10011 for guidance. Include number and percentage of subjects for each assessment. Footnote: Note: percentage is calculated using number of subject remaining in the study at given timepoint as denominator.	P-SAC [3], F-SAC [4]
6.008	All Treated	See programming notes	Summary of Compliance of EORTC QLQ-C30 and EORTC QLQ-MY20 by Visit (Part 2)	Report for: Part 2; Refer to mid205678 (primary_08) Table 8.10010 for guidance. Include number and percentage	P-SAC [3], F-SAC [4]

Health Outcomes: Tables					
No.	Population	IDSL / Example Shell	Title	Programming Notes	Deliverable [Priority]

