6.007	All Treated	See programming notes	Plot of Change from Baseline and Confidence Interval of EORTC QLQ-MY20 Disease Symptoms Domain Score by Visit (Part 2)	
Report for: Part 2; Refer to mid205678 (primary_07) Figure 8.10037 for guidance. Add a dashed line at y axis=0. In addition to treatment visits, also include end of treatment, worst case post treatment and last follow-up visits. Add arrows showing direction of change from baseline: "deterioration" "improvement". Add the following footnotes: Note 1: Interval shown represents 95% confidence limits around mean at each planned time. Note 2: "BSLN" represents "Baseline"; "EOT" represents "End of Treatment"; "WCPB" represents "Worst Case Post-baseline"; "LFU" represents "Last Follow-up".
	P-SAC [3], F-SAC [4]

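### The QLQ-C30 and QLQ-MY20 tables count subjects who improve by 10 points or more but not those who deteriorate by as much

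*SAP*

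**What the plan says.** **Threshold counts.** The programming note for Table 6.005 (SAP Section 16.11.12) reads "Including score for 15 domains and Improvement in EORTC QLQ-C30 domain score >=10". The note for Table 6.006 reads "Including score for 4 domains and Improvement in EORTC QLQ-MY20 domain score >=10". Sections 13.3.1 and 13.3.2, which describe the analyses in prose, mention no threshold, so the 10-point count exists only in these notes.

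**Important difference.** Section 16.6.5.1 cites a study of breast and small-cell lung cancer patients. Its figure for the mean QLQ-C30 shift is worded "between baseline and follow-up was about 5 to 10 points on a 0-100 scale for patients who indicated", and the patients meant are those who rated themselves as slightly changed. On direction, the same sentence covers "change on the Subjective Significance Questionnaire (SSQ), either for better or for worse". Section 16.6.5.2, on the QLQ-MY20, has no such text.

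**Other QLQ displays.** For the QLQ-C30, Section 13.3.1 says: "Descriptive summaries (mean, SD, median, min and max) of the actual value and change from baseline at selected time points will be provided". Section 13.3.2 asks for value and change by visit in each of the four QLQ-MY20 domains. Both sections plan plots of mean change over time and "at end of study treatment, last follow-up, and worst case post-baseline for individual domains will also be provided". The display list carries four of these: QLQ-C30 Fatigue, Global Health Status and Physical Functioning, and QLQ-MY20 Disease Symptoms (Figures 6.004 to 6.007). Listings 1.0059 and 1.0060 give all scores.

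**OSDI.** Section 13.2.2 counts the other direction for the vision-related domain: "the number and percentage of participants with post-baseline score worsening of ≥ 12.5 from baseline score will be summarized". Table 6.003 implements this.

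**The concern.** The one interpretive source in the SAP for a change of this size on the QLQ-C30 runs in both directions, but the tables turn only the favourable direction into a count. The SAP counts a threshold worsening for the OSDI, so the approach is already in use in this study.

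Part 2 is single-arm with about 28 subjects, and these two questionnaires are analysed in Part 2 only. A percentage improved by at least 10 points has no control group to set it against. Individual scores vary between visits, so some subjects cross a 10-point line when nothing has changed on average. The percentage crossing the line the other way is the natural figure to read beside it. The Part 2 exploratory objective concerns the effect of the combination on symptoms and quality of life in either direction, and a reader of the tables would want both shares.

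**Working it through.** The SAP states no SD, correlation or expected responder share for these scales, so there is no planned figure to reproduce. The check has two parts.

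**1. What the displays give in each direction**

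| Display | Improvement | Deterioration |
|---|---|---|
| Mean, SD, median, min and max of change (Tables 6.005, 6.006) | yes, signed | yes, signed |
| Mean-change plots with worst case post-baseline (Figures 6.004 to 6.007) | four domains | four domains |
| Score listings (1.0059, 1.0060) | yes | yes |
| Number of subjects past 10 points (Tables 6.005, 6.006) | yes | not specified |
| OSDI, number past 12.5 points (Table 6.003) | recovery after worsening | yes |

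The gap is one cell: the QLQ threshold count for deterioration.

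**2. How large an improved share can be without a mean effect (illustration)**

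Assume change is normal with mean m (positive means better) and SD s. Then

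- share improved = 1 − Φ((10 − m)/s)
- share deteriorated = Φ((−10 − m)/s)

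The value of s is an assumption, taken as 15 to 25 points.

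| m | s | Improved by ≥10 | Deteriorated by ≥10 |
|---|---|---|---|
| 0 | 15 | 1 − Φ(0.667) = 25.2% | 25.2% |
| 0 | 20 | 1 − Φ(0.500) = 30.9% | 30.9% |
| 0 | 25 | 1 − Φ(0.400) = 34.5% | 34.5% |
| −5 | 20 | 1 − Φ(0.750) = 22.7% | Φ(−0.250) = 40.1% |

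With all 28 subjects contributing and s = 20, no mean change gives 28 × 0.309 ≈ 9 improved and 9 deteriorated. A mean worsening of 5 gives 28 × 0.227 ≈ 6 improved and 28 × 0.401 ≈ 11 deteriorated. Under the present specification only the first number of each pair is tabulated.

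**Sensitivity to the SD.** Write s = SD × √(2(1 − r)), where SD is the SD of the score and r the correlation between baseline and visit. With SD from 10 to 30 and r from 0.3 to 0.9, the share improved at m = 0 runs from 1.3% (SD 10, r 0.9) to 38.9% (SD 30, r 0.3). Exactly 30% needs s = 10/0.524 = 19.1.

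**Sensitivity to the score steps.** A domain score moves in steps of 100/(items × range). Take a range of 3, which Section 16.6.5.1 gives for most QLQ-C30 items and which is assumed here for the QLQ-MY20. Count a change when the latent value passes the midpoint below the first attainable step of 10 or more. With m = 0 and s = 20:

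- single item (such as Body Image): step 33.3, cut 16.7, 1 − Φ(0.833) = 20.2%
- Disease Symptoms (6 items listed): step 5.56, first step past 10 is 11.1, cut 8.33, 1 − Φ(0.417) = 33.8%
- Side Effects of Treatment (10 items listed): step 3.33, threshold 10.0, cut 8.33, 33.8%
- Future Perspective (read as 3 items): step 11.1, cut 5.56, 1 − Φ(0.278) = 39.1%

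So the improved share expected from variation alone differs by domain. With a symmetric distribution and no mean change, though, it equals the deteriorated share whatever the SD or step.

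**The case against.** The strongest reply is that nothing is hidden. Tables 6.005 and 6.006 are change-from-baseline summaries, and the improvement count is an addition to them. A zero or negative mean change would stand in the same table. Patient-reported harm is also counted elsewhere, through the PRO-CTCAE maximum scores and the OSDI. This stands, and it limits the point. A reader might infer that meaningful deterioration is invisible, or that the QLQ-MY20 side-effects domain would show only improvers. The SAP does not support either reading: value and signed change are planned for every domain, and the listings give every score. Still, a mean, a median and the extremes do not say how many subjects worsened by 10 points.

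A reader might also infer that the tables break a rule the SAP sets for itself. They do not. The text in Section 16.6.5.1 is background on mean changes in other cancers, prescribes no responder analysis and concerns the QLQ-C30 only. Nothing says that the 10-point rows derive from it, and carrying it to the QLQ-MY20 is inference, although Table 6.006 uses the same cut-off. The OSDI, for its part, targets an expected eye toxicity, so counting worsening there has its own reason.

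It is tempting, too, to say that noise alone yields about 30% improved. That figure needs an SD of change near 19, which the SAP does not give.

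Finally, both tables point to another study's shells for guidance. Those are not at hand and could contain a deterioration row. The SAP itself names none, and naming it would settle the matter.

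**Conclusion.** The point holds in a limited form. The QLQ-C30 and QLQ-MY20 threshold counts are specified for improvement only, and the share of subjects deteriorating by 10 points or more is not specified anywhere in the SAP. In a single-arm study this leaves the improved percentage without the figure that would help a reader judge it.

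The size is illustrative: about 25% to 34% improved, and as many deteriorated, with no true mean change. It assumes an SD of change of 15 to 25 points and a normal approximation that ignores the score steps; other inputs move it widely, as shown above. The argument for a symmetric count does not depend on the exact value.

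Severity is minor. The endpoint is exploratory and descriptive, no decision in the SAP rests on it, and deterioration can be seen in other displays.

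**What to change.** In the programming notes for Tables 6.005 and 6.006, replace the single improvement count with three exclusive categories per domain and visit: improved by at least 10, changed by less than 10, deteriorated by at least 10. Use one denominator, the subjects with both a baseline score and a score at that visit, and print it.

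Take the direction from what the SAP already states. By Section 13.3.1, higher is better for the QLQ-C30 functional scales and global health, and lower is better for its symptom scales and single items. By Section 16.6.5.2, higher is better for Future Perspective and Body Image, and lower is better for Disease Symptoms and Side Effects of Treatment.

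The cost is two extra rows per domain at each visit: 15 × 2 = 30 in Table 6.005 and 4 × 2 = 8 in Table 6.006. No new data are needed and no other analysis changes.
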